7.9.2 Visit Windowing

Data will be summarized based on nominal visit indications with the exception of data captured at early termination and unscheduled visits. Data from early termination and unscheduled visits will be summarized based on mapped visit values. The analysis windows for early termination and unscheduled visits are presented in the following table.

Analysis Windows for Efficacy and Safety Assessments

Scheduled Visit	Target Study Day	Window (Days)
Day 8	8	5 to 11
Day 15	15	12 to 18
Day 22	22	19 to 25
Day 29	29	26 to 32

Data collected at early termination and unscheduled visits prior to study day 5 will not be analyzed, with the exception of those identified as baseline values. Data collected at early termination and unscheduled visits after study day 32 will not be included in analyses.

The definition for the study day included in each study window is defined as below:

Study Day Prior to Day 1 = Visit Date – Day 1 Date

Study Day On or After Day 1 = Visit Date – Day 1 Date + 1

If an assessment's mapped visit is a visit at which the subject has data present, or if no analyses are planned for the assessment at the mapped visit, the data collected at the early termination or unscheduled visit will not be included in analyses.

In the event of multiple values from unscheduled or early termination assessments within an analysis window, the value closest to the scheduled visit target study day will be used for analyses. If two values tie as closest to the time point (for example, one value is before and the other value is after the time point), then the later value will be selected.

Data collected at all visits will be included in the data listings.

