6.23.2 Blood Volumes

Total blood volume (TBV) is related to body weight. The TBV of a child is about 75-80 mL/kg. Existing guidelines for blood sample volume limits (ranging from 1–5% of total blood volume within 24 hours and up to 10% of total blood volume over 8 weeks) are consistent with the limited evidence available on “minimal risk” to children (Howie, 2010).

In this study, the smallest volume of blood will be collected for analysis of safety and PK. A total of approximately 29.5 mL will be collected over the study period.

Blood samples are scheduled to be collected ten (10) times over the course of the study. Additional blood samples may be collected for evaluation of safety as clinically indicated.

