7.7 Unscheduled Visit(s)

An unscheduled visit will be scheduled every 7 to 14 days in order to follow-up on unresolved adverse events that were still present at the final visit (V6). Additionally, the Study subject may be asked to return for additional visits to follow clinically significant abnormal laboratory results.

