7.9.9.3 Clinical Laboratory Evaluations

Laboratory test results will be summarized with descriptive statistics at Baseline and Day 29. Additionally, change from baseline values will be summarized at Day 29, and shifts from Baseline to Day 29 in laboratory test results based on normal ranges will be summarized with frequency counts and percentages. Individual laboratory test results, including urine and serum pregnancy test results, will be presented in a by-subject listing.

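### Post-baseline early-termination and unscheduled labs before Day 26 enter no lab table, and the SAP specifies no subject count for clinically meaningful change in ECG or vital signs

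*SAP*

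**What the plan says.** SAP 7.9.2 analyses scheduled visits under their nominal label and maps ET and unscheduled values to windows: Days 5 to 11 for Day 8, 12 to 18 for Day 15, 19 to 25 for Day 22, and 26 to 32 for Day 29. Four rules then exclude values from analysis:

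- Early values: "Data collected at early termination and unscheduled visits prior to study day 5 will not be analyzed", except those that serve as baseline.
- Late values: "Data collected at early termination and unscheduled visits after study day 32 will not be included in analyses".
- Values that map to an occupied visit. The condition reads "If an assessment's mapped visit is a visit at which the subject has data present".
- Values that map to a visit with no planned analysis: "if no analyses are planned for the assessment at the mapped visit, the data collected at the early termination or unscheduled visit will not" enter the analyses.

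All values stay in the listings.

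For labs, SAP 7.9.9.3 states: "Laboratory test results will be summarized with descriptive statistics at Baseline and Day 29". Change from baseline is also summarised at Day 29 only, and "shifts from Baseline to Day 29 in laboratory test results based on normal ranges will be summarized with frequency counts and percentages".

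The protocol provides for labs outside the schedule. Section 6.23.2: "Additional blood samples may be collected for evaluation of safety as clinically indicated". Section 7.7: "the Study subject may be asked to return for additional visits to follow clinically significant abnormal laboratory results". Section 7.6 collects safety labs at V6 or at early termination.

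SAP 6.3.2 lists as a secondary safety endpoint the incidence of clinically meaningful change from baseline in labs, ECG and vital signs. SAP 7.9.9.4.1 and 7.9.9.4.2 give ECG and vital signs descriptive statistics and change from baseline by visit. Protocol 11.5.1 foresees frequency tables where appropriate for these domains and leaves the detail to the SAP.

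**The concern.** The protocol visit descriptions (sections 7.1 to 7.6) collect safety labs at Screening, V2 and V6/ET only. For a subject who leaves early, the ET sample is the only scheduled post-baseline lab. Protocol 4.6.1.1 encourages such a subject to attend that visit, yet the SAP then leaves the result out of every lab table if the visit falls before Day 26.

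In subjects who reach Day 29 the exclusion works differently. An unscheduled lab drawn because something looked wrong on, say, Day 18 has no analysis visit to map to, and the Day 29 value alone represents the subject. If the abnormality has resolved by Day 29, the shift table shows nothing.

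The Day 29 shift table is the only lab frequency table that the SAP specifies, so these exclusions decide what it can show. The second gap is separate: an endpoint worded as an incidence needs a count of subjects, and for ECG and vital signs the SAP specifies none.

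**Working it through.** **Inputs.** Windows and exclusion rules: SAP 7.9.2. Post-baseline visits with a planned summary: labs Day 29 (SAP 7.9.9.3); ECG Days 15 and 29 (7.9.9.4.1); vital signs other than weight Days 8, 15, 22 and 29 (7.9.9.4.2). V6 at Day 29 ± 1: protocol schedule. Follow-up every 7 to 14 days for adverse events unresolved at V6: protocol 7.7. About 45 registered for 32 completed: SAP 4.1.

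**Step 1: the Day 26 boundary.** The Day 22 window ends on Day 25 and the Day 29 window opens on Day 26. Crossing the windows with the planned summaries shows where a post-baseline ET or unscheduled value can enter:

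| Study day | Mapped visit | Labs | ECG | Vital signs |
|---|---|---|---|---|
| up to 4 | none | no | no | no |
| 5–11 | Day 8 | no | no | yes* |
| 12–18 | Day 15 | no | yes* | yes* |
| 19–25 | Day 22 | no | no | yes* |
| 26–32 | Day 29 | yes* | yes* | yes* |
| after 32 | none | no | no | no |

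*Only if the subject has no data already at that visit.

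**Step 2: subjects who leave before Day 26.** Possible ET days are Days 2 to 25, that is 25 − 2 + 1 = 24.

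- Labs: 0 of 24.
- ECG: Days 12 to 18, 18 − 12 + 1 = 7, so at most 7 of 24.
- Vital signs: Days 5 to 25, 25 − 5 + 1 = 21, so at most 21 of 24.

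**Step 3: subjects with a Day 29 lab.** Days 2 to 32 are 31 days. On Days 2 to 25 (24 days) no lab analysis applies. Days 26 to 32 (7 days) are blocked because Day 29 is occupied. 24 + 7 = 31, so an unscheduled lab can enter on 0 of 31 days. The first adverse-event follow-up visit after V6 falls between Day 28 + 7 = 35 and Day 30 + 14 = 44, past the Day 32 cut-off.

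**Step 4: subjects.** The planned gap is 45 − 32 = 13, and 13/45 = 28.9%. The documents do not say when these subjects leave. If k of 45 leave before Day 26, the share with no post-baseline lab in any lab table is k/45: 0 gives 0%, 4 gives 8.9%, 7 gives 15.6%, 13 gives 28.9%. These values of k are assumptions.

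**Step 5: what one value can do (assumed case).** If none of 32 completers shifts and one leaver's ET lab does, the planned table shows 0/32 = 0%; with the ET value it would show 1/33 = 3.0%.

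**Step 6: endpoint against analysis.**

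| Domain | Specified in the SAP | Count of clinically meaningful change |
|---|---|---|
| Labs | descriptive, change, normal-range shift at Day 29 | no; the shift is a partial substitute |
| ECG | descriptive, change at Days 15 and 29 | no |
| Vital signs | descriptive, change by visit | no |

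None of the three domains has the count that the endpoint names, and neither document defines clinically meaningful.

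**The case against.** The best defence is that nothing is lost. SAP 7.9.2 keeps all visits in the listings. An abnormal laboratory finding can be an adverse event (protocol 10.1), and the TEAE tables in SAP 7.9.9.2 count subjects without visit windows. Subjects who stop treatment should stay in the study (protocol 4.6.1.1), and SAP 7.1 includes their later data. A DSMB reviews safety. The study is small, open-label and descriptive, and its primary endpoint is pharmacokinetic.

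Most of this stands and limits the point. A reader might infer that these safety data disappear altogether; the listings and TEAE tables show otherwise. A reader might also infer that every unscheduled lab is excluded. That is not so: a pre-dose repeat can be the last non-missing value and serve as Baseline (SAP 7.9.1 and the exception in 7.9.2), and a value on Days 26 to 32 enters if Day 29 is empty. What remains is that a listing gives no incidence, and that TEAE tables depend on reporting and apply no change-from-baseline criterion.

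On the endpoint, protocol 11.5.1 does foresee frequency tables, and SAP section 5 declares no change to planned analyses. It would therefore be too strong to say that the protocol plans no counts. But 11.5.1 sets no criterion and passes the detail to the SAP, which gives none for ECG or vital signs.

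A worst-value table with no time limit would bring its own problem: protocol 6.24.1 allows other therapy after the study, so late values could reflect that therapy. The remedy needs a cut-off.

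**Conclusion.** The point holds for post-baseline values. ET and unscheduled labs before Day 26 enter no lab summary, change or shift table, and a subject with a Day 29 lab contributes no post-baseline unscheduled lab on any day. A subject who leaves before Day 26 is missing from all post-baseline lab tables, whether or not the ET sample was taken. This follows directly from the stated rules and needs no assumption.

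The number of subjects affected cannot be derived. Reading 28.9% as the expected loss would be wrong: it assumes that all 45 are dosed and that all 13 of the planned gap leave before Day 26, and the ET rule discards a result only where an ET lab was drawn. The day counts describe the rule and do not estimate how many results will be lost.

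The endpoint gap also holds, as a matter of specification: no subject count for ECG or vital signs, and a partial substitute for labs. The windowing half is the firmer one, because there a written rule discards data already collected. Neither half touches the pharmacokinetic analysis. This should be fixed because it is cheap and improves the safety report; it does not invalidate the study.

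**What to change.** 1. Keep the by-visit windows, and state in SAP 7.9.2 that they do not apply to any-post-baseline safety summaries.
2. In SAP 7.9.9.3, add a shift from Baseline to the worst post-baseline lab value, with low and high directions shown separately. Use scheduled, ET and unscheduled values from first dose to a cut-off pre-specified in the SAP, and show later follow-up values separately. Report the number of subjects with no post-baseline value.
3. Add n (%) of subjects with any post-baseline change that meets sponsor criteria for labs, ECG and vital signs. Fix the criteria in the SAP before database lock, which protocol 11.3.1 already sets as the deadline for the SAP. If the investigator's rating of clinical relevance (protocol 4.7.2) is used for labs, apply it only to abnormalities that are new or worse than baseline, because it rates abnormal values and not change.

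Cost: SAP text, a few added tables, and criteria that the sponsor must write. No new visits or samples are needed. The investigator's rating is documented on the laboratory report, so it would have to be captured as data if it is used.

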7.9.3 Subject Disposition

The number of subjects included in each analysis population (ITT and safety), as well as the number of subjects in the safety population with PK data will be summarized. The number of subjects treated, completed, discontinued treatment (including the reason for treatment discontinuation), and discontinued study (including the primary reason for study discontinuation) will be presented.

Subjects who are excluded from an analysis population will be summarized by the reasons for exclusion.

7.9.4 Protocol Deviations

Protocol deviations will not be entered into the database and therefore will not be summarized.

7.9.5 Demographic and Baseline Characteristics

All baseline summaries will be done on the ITT and safety populations.

Sex, race, ethnicity, Fitzpatrick skin type, dietary habits, and alcohol, tobacco and drug use will be summarized by counts and percentages. Age, height, and weight will be summarized with descriptive statistics (n, mean, SD, median, min, and max).

Atopic dermatitis history, including family history of atopic dermatitis, location of disease, and diagnoses of allergic rhinitis and asthma, will be summarized by counts and percentages.

Medical histories will be coded using the MedDRA dictionary and will be summarized by MedDRA system organ class and preferred term.

7.9.6 Prior and Concomitant Medications

Prior and concomitant medications will be coded to preferred term and anatomical therapeutic chemical (ATC) classification of ingredients using the WHO-DDE.

Counts and percentages will be provided to summarize the use of medications other than the study drug reported throughout the study. The number and percent of subjects reporting medications will be summarized by ATC level 2 term and preferred name. Medications which start prior to first dose will be considered prior medications, and medications which start on or after first dose will be considered concomitant medications. Medications with incomplete start dates which could be prior to first dose or after first dose will be considered concomitant.

Skin care products used during the study and prior and concomitant procedures and therapies will be included in by-subject listings.

7.9.7 Pharmacokinetic Analyses

The pharmacokinetic analysis will be conducted using non-compartmental analysis on plasma concentrations of MM36 and its metabolites (MAP-15484, MAP15497 and MAP-15485) in the subjects in the safety population who have PK data.

Individual plasma concentrations of MM36 and its metabolites will be summarized descriptively at Day 1 and Day 15 using the arithmetic mean, SD, CV%, median, min, and max. Individual plasma concentration-time profiles of MM36 and its metabolites will be plotted on both a linear and a semi-logarithmic scale at each visit. Mean values will also be presented graphically.

Plasma concentrations below the lower limit of quantitation (BLQ) (< 0.2 ng/mL) will not be considered quantifiable concentrations. BLQ values and quantifiable concentrations will be

summarized separately using summary statistics. Any quantifiable concentrations at pre-dose at Day 1 will be set to zero in both concentration summaries, as well as in PK parameter calculations. Plasma concentration-time profiles will display BLQ values as 0 ng/mL on the linear scale, and will omit BLQ values on the semi-logarithmic scale.

The following pharmacokinetic parameters will be analyzed for each subject at Day 1 and Day 15 if there are a sufficient number of quantifiable concentrations of MM36 or its metabolites to permit their derivation.

C_{\max}	Maximum plasma concentration C_{\max} = BLQ if concentrations are BLQ at all time points
T_{\max}	Time of maximum plasma concentration T_{\max} will be calculated if at least one quantifiable plasma concentration is detected in the time interval. Individual elapsed sampling times will be used. If the maximum concentration is observed pre-dose, T_{\max} will be considered 0 hours.
$AUC_{0-\text{last}}$	Area under the plasma concentration-time curve from time zero to the time of last quantifiable plasma concentration $AUC_{0-\text{last}}$ will be calculated if at least two consecutive quantifiable plasma concentrations are detected in the time interval. Area will be computed using the linear trapezoidal rule with individual elapsed sampling times and observed concentrations. BLQ values will be set to zero before T_{\max} and missing after T_{\max} .

Descriptive summary statistics (n, arithmetic mean, SD, CV%, median, min, max, and GM) will be reported for PK parameters. Individual plasma concentrations and PK parameter values will be included in by-subject listings.

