11.3 Statistical Analysis

11.3.1 General Statistical Methodology

- All statistical processing will be performed using SAS® unless otherwise stated.
- Continuous data will be summarized using descriptive statistics (number of values, mean, standard deviation, median, minimum and maximum). Categorical data will be summarized using frequency tables (frequencies and percent).
- A statistical analysis plan (SAP), describing all statistical analyses will be provided as a separate document. The SAP will be finalized prior to locking the database. The SAP will contain any modifications to the analysis plan presented below.

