11.4 Primary Analysis

11.4.1 Pharmacokinetics

Individual plasma concentrations of MM36 and its metabolites (MAP-15484, MAP15497 and MAP-15485) will be summarized descriptively using the arithmetic mean, standard deviation (SD), CV (%), median, minimum and maximum. Individual plasma concentration-time profiles of MM36 will be plotted on both a linear and a semi-logarithmic scale. Mean values will also be presented graphically. The following pharmacokinetic parameters will be analyzed for each subject and for each PK time point at which a sufficient (detectable) concentration of MM36 or its metabolites will be measured to permit their derivation. If there are sufficient concentration data above the level of quantitation the following pharmacokinetic parameters will be calculated:

- C_{max} = Maximum plasma concentration
- T_{max} = Time of maximum plasma concentration
- AUC_{0-last} = Area under the plasma concentration-time curve from time zero to time last (time of last quantifiable plasma concentration) [AUC_{0-t}]

The pharmacokinetic analysis will be implemented in SAS®, and conducted using Non-Compartmental Analysis (NCA) on plasma concentrations of MM36 in the subjects who will receive MM36 1% ointment and had evaluable plasma concentration-time profiles. PK parameters will be listed for all individuals. Descriptive summary statistics (number of observations (N), arithmetic mean, standard deviation (SD), CV%, median, minimum, maximum and geometric mean) will be reported for PK parameters. Individual elapse sampling time will be used in the pharmacokinetic analysis. C_{max} and t_{max} will be obtained directly from the experimental observations. $AUC_{(0-t)}$ will be calculated using the linear trapezoidal rule.

BLQ (< 0.2 ng/mL) samples will be set to zero for the summary of the statistics for concentration values. For the purpose of the NCA, BLQ set to zero before t_{max} and missing after t_{max} . Any quantifiable concentrations at pre-dose at Day 1 will be set to zero.

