5. CHANGES IN THE CONDUCT OF THE STUDY OR PLANNED ANALYSES

There are no changes in the conduct of the study or planned analyses.

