7. STATISTICAL METHODS AND ANALYSIS

7.1 General Methodology

All analyses will be performed by Confidential The standard operating procedures of Confidential will be followed in the creation and quality control of all data displays and analyses.

Efficacy analyses will be performed for the intent-to-treat (ITT) population and safety and PK analyses will be performed using the safety population.

All analyses will be performed using SAS® Version 9.3 or later. Continuous data will be summarized using descriptive statistics (number of values [n], mean, standard deviation [SD], median, minimum [min], and maximum [max]). Additional summary statistics, coefficient of variation (CV%) and geometric mean (GM), will be included for PK data summaries. PK concentration summaries will include CV%, and PK parameter summaries will include both CV% and GM. Categorical data will be summarized using frequency tables (frequencies and percents).

Reported AEs, medical history terms, and prior and concomitant procedures and therapies will be classified on the basis of Medical Dictionary for Regulatory Activities (MedDRA) terminology, Version 19.1. Prior and concomitant medications and skin care products will be classified on the basis of World Health Organization Drug Dictionary (WHO-DDE) terminology, Format B2, Version March 1, 2016.

Data collected at a time point will be summarized regardless of treatment with study drug. Post-treatment assessments for subjects who discontinue treatment but continued to be followed in the study will be included in summaries.

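### The protocol and SAP treat below-quantitation concentrations differently in the primary PK summary, and the SAP declares no change

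*SAP*

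**What the plan says.** The primary endpoint is the plasma concentration of MM36 and its metabolites after the first application and after two weeks. The analysis is descriptive: mean, SD, CV%, median, minimum and maximum.

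- **Protocol 11.4.1.** BLQ means below 0.2 ng/mL. Such "samples will be set to zero for the summary of the statistics for concentration values". They therefore enter the same mean, SD, CV% and median as the quantifiable values.
- **SAP 7.9.7.** Here the BLQ results and the quantifiable results are "summarized separately using summary statistics. Any quantifiable concentrations at pre-dose at Day 1 will be set to zero in both concentration summaries". The zero in the second sentence applies to quantifiable Day 1 pre-dose values, not to BLQ values.
- **Where the SAP does give BLQ a number.** Profiles "will display BLQ values as 0 ng/mL on the linear scale" and omit them on the semi-logarithmic scale. For AUC0-last, BLQ is zero before Tmax and missing after it, which agrees with the protocol.
- **Cmax in SAP 7.9.7.** Cmax is "BLQ if concentrations are BLQ at all time points". SAP 7.1 adds: "PK concentration summaries will include CV%, and PK parameter summaries will include both CV% and GM".
- **Recording of changes.** Protocol 11.3.1: "The SAP will contain any modifications to the analysis plan presented below". SAP Section 5: "There are no changes in the conduct of the study or planned analyses".

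**The concern.** A pooled summary with BLQ at zero and a summary split by quantifiability are different analyses of the same samples. The protocol allows the SAP to depart from it, but the SAP says it has not done so. A programmer therefore cannot tell whether the protocol's rule still applies, and two programmers could produce different primary tables.

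The study has no hypothesis test and no inferential sample size, so these summary statistics are the primary result. If the mean covers quantifiable samples only, average exposure under maximal use is overstated. The CV% is usually understated as well, because the low values are removed. If the quantifiable share differs between Day 1 and Day 15, the two columns describe different subsets of children, although no formal comparison is planned. The issue applies to MM36 and to each of its three metabolites.

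The Cmax gap has the same root. A text value cannot enter a mean or geometric mean, so children with no quantifiable sample drop out of the parameter summary unless a number is stated for them.

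**Working it through.** **Inputs.** The limit of quantitation is 0.2 ng/mL (protocol 11.4.1, SAP 7.9.7) and the planned number is 32 subjects (protocol 11.1, SAP 4.2). Neither document gives a BLQ share or an expected concentration, so p, m and the distributions below are assumptions. The plan has no figure of its own to reproduce.

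**Bounds without a distribution.** Let p be the BLQ share and m the mean of the quantifiable samples. Each BLQ sample truly lies between 0 and 0.2, so:

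- mean with BLQ = 0: (1 − p)m, which is also the lower bound of the true mean;
- upper bound of the true mean: (1 − p)m + 0.2p;
- quantifiable-only mean ÷ BLQ = 0 mean: 1/(1 − p).

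With m = 0.45 ng/mL:

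| p | (1 − p)m | (1 − p)m + 0.2p | Quantifiable-only mean ÷ true mean |
|---|---|---|---|
| 0 | 0.45 | 0.45 | 1.0 |
| 25% | 0.3375 | 0.3875 | 1.16 to 1.33 |
| 50% | 0.225 | 0.325 | 1.38 to 2.0 |
| 75% | 0.1125 | 0.2625 | 1.7 to 4.0 |

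Setting BLQ to zero errs low, by at most 0.2p: 0.05, 0.10 and 0.15 ng/mL for the last three rows.

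**Median and CV%.** With more than half the samples BLQ, the median is 0 under the protocol and at least 0.2 among quantifiable values. As a small example, take four BLQ samples and four at 0.3, 0.5, 0.8 and 1.2 ng/mL. With BLQ at zero (n = 8), the mean is 2.8/8 = 0.35, the CV 130% and the median (0 + 0.3)/2 = 0.15. With quantifiable values only (n = 4), the mean is 2.8/4 = 0.70, the CV 56% and the median 0.65.

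**Dependence on concentration level.** Assume lognormal concentrations with a CV of 100% (log-scale SD √ln 2). Means are in ng/mL.

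| Geometric mean | BLQ share | True mean | BLQ = 0 | BLQ = 0.1 | Quantifiable only |
|---|---|---|---|---|---|
| 0.1 | 80% | 0.141 | 0.071 | 0.150 | 0.349 |
| 0.2 | 50% | 0.283 | 0.226 | 0.276 | 0.451 |
| 0.4 | 20% | 0.566 | 0.539 | 0.559 | 0.675 |
| 1.0 | 2.7% | 1.414 | 1.410 | 1.413 | 1.449 |
| 2.0 | 0.3% | 2.828 | 2.828 | 2.828 | 2.836 |

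At a geometric mean of 1.0 the quantifiable-only mean is 1.449/1.414, or 2.5% high. At 2.0 it is 0.3% high.

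**Cmax.** Suppose 8 of 32 children have only BLQ samples and the other 24 have a Cmax of 0.5 ng/mL. Dropping the 8 gives a mean and a geometric mean of 0.50. Keeping them at half the limit (0.1) gives a mean of (24 × 0.5 + 8 × 0.1)/32 = 0.40 and a geometric mean of 0.5^0.75 × 0.1^0.25 = 0.33.

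**The case against.** The strongest reply is that the SAP is unclear rather than in conflict with the protocol. A split summary cannot be carried out as written, because BLQ values have no number from which to compute statistics. The mention of two concentration summaries may mean one table of all samples and one of quantifiable samples, and the abbreviation list defines a count of quantifiable concentrations that would suit such a layout. With no change declared, the protocol's zero would then carry over. This reading is possible, but the text does not settle it. The word for two may simply link the summaries to the parameter calculations, and the count is never used in 7.9.7. Even on this reading the SAP leaves the tabular value of BLQ unstated.

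The reply is also right that the effect may be small. The illustrations with m = 0.45 sit close to the limit, the assay range runs to 40 ng/mL, and above about 1 ng/mL the difference is minor. The maximum (given at least one quantifiable value) and the by-subject listings do not change, the AUC rules agree, and a reader with the listings could recover the pooled mean as m times the quantifiable fraction. These points limit the seriousness; they do not supply the missing rule.

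Two further points stand. The Cmax gap is not a disagreement between the documents, since the protocol has no rule for it either. And neither document calls for a sensitivity table, so that part of the remedy is the more optional one.

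**Conclusion.** The concern holds. The protocol and SAP do not give the same rule for BLQ samples in the primary descriptive summary, the SAP assigns no tabular value, and Section 5 reports no change. Followed literally, the SAP yields a quantifiable-only mean that exceeds the protocol's by 1/(1 − p) and exceeds the true mean whenever a post-dose sample is BLQ.

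The size depends entirely on the BLQ share, which the documents do not give. It is nil with no BLQ samples, a few percent or less if typical concentrations are 1 ng/mL or above (under the lognormal assumption), and 1.38- to 2-fold relative to the true mean if half the samples are BLQ and the quantifiable mean is 0.45 ng/mL. This should be fixed, and before the BLQ rate is known, so that the choice of rule cannot depend on the data.

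**What to change.** State one rule in both documents.

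1. **Primary concentration table.** At each time point keep every sampled subject in the denominator, report the number sampled and the number quantifiable, and set BLQ to zero as the protocol does. Use the same rule for the mean plot on the linear scale.
2. **Sensitivity table.** Because zero errs low, add one table with BLQ at half the limit (0.1 ng/mL). A footnote can give the upper bound of the mean: the BLQ = 0 mean plus 0.2 times the BLQ share.
3. **Cmax.** Keep children with only BLQ samples in the summary and report how many there are. Within a table, use the same substituted value for the arithmetic and geometric means. Give no geometric mean in the BLQ = 0 table if any Cmax is zero; give it in the half-limit table.
4. **Separate summaries.** Replace the sentence in SAP 7.9.7. If a quantifiable-only table is wanted, label it as additional and record it in SAP Section 5.

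The cost is a few sentences and one extra table, with no new data. Reported means will be lower than quantifiable-only means if any sample is BLQ, and unchanged if none is.
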